3.2 Feasibility

In order to carry out this research project, work will be carried out at the facilities of the Anáhuac México Norte University, at the Kidney Specialty Center (State of Mexico) and at the Nueva Oxtotitlán clinic (Toluca), where the tests will be carried out with the patients. The equipment to carry out the electrophysiology tests (electrical recording and stimulation) is already available, as well as the cocoa capsule supplement, so the study can be carried out without setbacks. Cocoa supplementation does not affect the patients' dietary regimen or compromise their regular medication. In addition, the RDD of the H reflex test does not produce adverse effects, is painless and noninvasive.

4. STATEMENT OF THE PROBLEM

T2D is associated with the development of chronic-degenerative complications such as diabetic peripheral and autonomic neuropathy. This manifests itself as a set of disorders that occur as a consequence of a chronic state of hyperglycemia that favors a state of inflammation and oxidative stress, resulting in damage to the peripheral and autonomic nervous system.

This hyperglycemia contributes to the increase in the inflammatory state and the production of reactive oxygen species, as well as to the increase in oxidative phosphorylation and overload of the electron transport chain. Among the cells that are most affected are the Schwann cells, which, when damaged, cause alterations in the functioning of the axons and nerve fibers.

Flavonoids are phenolic compounds present in foods such as cocoa, and whose effects are recognized as antioxidant and anti-inflammatory mechanisms. Additionally, in preclinical studies, their consumption has been associated with a decrease in hyperglycemia and insulin resistance, improvement in mitochondrial function and attenuation of autonomic diabetic neuropathy, so they could be very useful in these patients.

The Hoffman reflex objectively and noninvasively assesses the response of the somatosensory system. A study in subjects with T1D reported that the H reflex evoked by paired pulses in the lower extremities may be an indicator of dysfunction in somatosensory processing at the spinal level. To date, few studies have evaluated the dysfunction of sensory and autonomic fibers simultaneously in DN, so this study would provide valuable data since it additionally includes the evaluation of markers related to oxidative stress and inflammation, in addition to considering the evaluation of symptoms reported by subjects with peripheral and autonomic DN during 3 months of cocoa supplementation through a double-blind, randomized controlled clinical trial.

5. RESEARCH QUESTION

What is the effect of cocoa supplementation on the biochemical and clinical profile and somatosensory processing of diabetic peripheral and autonomic neuropathy?

6. HYPOTHESIS

Cocoa supplementation has a beneficial impact on the biochemical and clinical profile and somatosensory processing of diabetic peripheral and autonomic neuropathy.

7. GENERAL OBJECTIVE

To evaluate the effect of cocoa supplementation on the biochemical and clinical profile, and somatosensory processing of diabetic peripheral and autonomic neuropathy during 3 months of treatment.

7.1 SPECIFIC OBJECTIVES

Biochemical profile:

- To evaluate the effect of cocoa supplementation on the glycemic profile (HbA1c and fasting blood glucose).
- To evaluate the effect of cocoa supplementation on lipid profile (triglycerides, HDL-c, LDL-c and TG/HDL).
- To evaluate the effect of cocoa supplementation on markers of inflammation (neutrophil/lymphocyte ratio).

Clinical profile:

- To evaluate the effect of cocoa supplementation on the “Toronto Clinical Scoring System” score.
- To evaluate the effect of cocoa supplementation on anthropometry (weight, waist and abdominal circumference, waist to height ratio).
- To evaluate the effect of cocoa supplementation on blood pressure.
- To evaluate the effect of cocoa supplementation on quality of life.
- To evaluate the effect of cocoa supplementation on gastrointestinal symptoms.

Somatosensory processing:

- To evaluate the effect of cocoa supplementation on sensorimotor processing in the spinal cord using the RDD of the H reflex test.

8. METHODOLOGY

8.1 Study Type: Explanatory

8.2 Design: Double-blind, randomized controlled clinical trial.

8.3 Study population: Adult subjects aged 40-60 years diagnosed with type 2 diabetes mellitus and diabetic neuropathy who attend, by open call, to Anáhuac México Norte University, the Kidney Specialty Center in the State of Mexico, and the Nueva Oxtotitlán clinic (Toluca).

8.4 Sample Size Calculation:

$$N = \frac{2(Z\alpha+Z\beta^2)s^2}{d^2} = N = \frac{2(1.96+0.84^2)(0.84)^2}{(0.776)^2} = N = \frac{(15.68)(0.7056)}{(0.6021)}$$

A total of 18 subjects per group were obtained, considering the following data:

s= Baseline standard deviation: 0.84 (obtained from a study in which probucol and methylcobalamin are used in subjects with DN and the TCSS is used to assess the effect of the intervention.) (49)

d= Proposed difference: 0.776 (refers to the expected difference → 7.5% decrease with respect to the control group)

Z α = 1.96 (value in tables, corresponding to a significance level of 95% for two tails)

Z β = 0.84 (value in tables, corresponding to a power of 80%)

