8.5 Selection criteria

Inclusion Criteria	Non-inclusion Criteria

 - Adults aged 40-60 years with a diagnosis of type 2 diabetes mellitus (T2D) and diabetic neuropathy - Minimum duration of T2DM diagnosis: 5 years. - MNSI (Michigan Neuropathy Screening Instrument) score ≥ 2. - Both genders. - Must sign the informed consent form 	
 - Subjects with known sensitivity or hyperreactivity to cocoa or any of its components. - Pregnant women. - Subjects with neurological diseases, such as multiple sclerosis, epilepsy, or previous cerebrovascular events. - Subjects with implanted electronic devices, e.g., pacemakers. - Subjects with peripheral nerve damage in the lower extremities caused by trauma.

	
 - Subjects with a diagnosis of disc herniation below T10. - History/diagnosis of herpes zoster. - Serological diagnosis of rheumatoid arthritis or systemic lupus erythematosus. HIV/AIDS. - Venous insufficiency (C2-C6 class, asymptomatic/symptomatic according to Nicolaides CEAP classification) in lower limbs. - Clinical hypothyroidism. - Use of orthopedic equipment (e.g., prosthetics, splints, wheelchair, crutches). - Cancer diagnosis, use of oncological drugs and/or radiotherapy, or history of cancer or tumors treated with oncological drugs or radiotherapy. - Smoking, considered positive in those with a smoking index greater than 10. - History of diabetic foot (Wagner Scale 3-5) or amputation. - Presence of ulcers and open and/or extensive wounds (>2 cm) - Allodynia - Sciatic nerve root compression - Gout/Hyperuricemia
--	---

Elimination Criteria

- Subjects who modify their pharmacological treatment during the study.
- Subjects who do not attend one of the intermediate consultations
- Subjects who withdraw informed consent or decide not to continue participating in the

study

- Subjects with less than 80% adherence to cocoa supplementation
- Subjects who miss more than one consultation or do not attend the final consultation.

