Patients will be asked to attend the appointments on an empty stomach, after having urinated and defecated. Weight will be determined according to the Lohman technique, that is, without shoes and with as few clothes as possible, the individual will be placed in the center of the scale and must remain still during the measurement. (54) Waist circumference will be measured according to the proposal of the Ministry of Health of Mexico: placing the tape in a horizontal plane around the waist, taking as reference the mid-axillary line, locating the midpoint between the lower costal margin and the highest lateral edge of the iliac crest (55) and the abdominal circumference: the upper part of the hip bone and the upper part of the right iliac crest are located and the measuring tape is placed in a horizontal plane around the abdomen, at the level of the iliac crest, at the end of a normal expiration. (55) Likewise, blood pressure will be measured using a sphygmomanometer (Nebucor brand, model HL-888JA), according to the Clinical Practice Guide for the Diagnosis and Treatment of Arterial Hypertension in the first level of care (57). These evaluations will be carried out every month, until completing the three months of the duration of the study. In addition, at the beginning of the study the MNSI (Annex 3) will be applied as part of the diagnosis of DN, and both at the beginning and at the end, the TCSS (Annex 4), the questionnaire as the physical examination (51), the BEST questionnaire (Annex 5), the Bristol scale (Annex 6) and the Diabetes 39 quality of life questionnaire (Annex 7) will be applied and laboratory studies will be taken to know the biochemical parameters (triglyceridemia, HDL-c, LDL-c, glycemia,

HbA1c, TG / HDL index and neutrophil/lymphocyte ratio will be determined, as described in the table of variables.

Participants in both groups, being subjects with a cardiometabolic disease, will be nutritionally assisted, that is, all patients will be given a meal plan according to the characteristics of each one of them, calculated by the Mifflin-St. Jeor energy expenditure prediction formula (67) for subjects with obesity, while, according to the Joslin Diabetes Center, a distribution of 40-45% carbohydrates, 30-40% lipids, and 20-30% protein is suggested. (68) Two capsules will be prescribed – cocoa for the experimental group or methylcellulose for the control group – in the morning and two capsules at night.

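### Section 8.4 states 18 per group for 80% power, but its own arithmetic gives 19 and the power at 18 is 77–79%; it also leaves open whether 18 is enrolled or evaluable and allows nothing for the eliminations in 8.5

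*Combined protocol and SAP*

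**What the plan says.** Section 8.4 of the combined protocol and SAP sizes the trial on the TCSS with the normal-approximation formula for two means. Its inputs are a two-sided 5% level (Z 1.96), Z 0.84 ("value in tables, corresponding to a power of 80" per cent), a difference of 0.776 and an SD of 0.84. The SD was "obtained from a study in which probucol and methylcobalamin are used in subjects with DN". The last printed line is (15.68)(0.7056)/(0.6021), and the result is given as: "A total of 18 subjects per group were obtained, considering the following data".

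Section 8.5 then lists five elimination rules. Besides withdrawal, they are:

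- "Subjects who modify their pharmacological treatment during the study"
- "Subjects who do not attend one of the intermediate consultations"
- "Subjects with less than 80% adherence to cocoa supplementation"
- "Subjects who miss more than one consultation or do not attend the final consultation"

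Section 8.7 collects "both at the beginning and at the end, the TCSS (Annex 4"), so each subject has a baseline and a final score. Section 8.8 compares the groups at each time point with an independent-samples t-test, or Mann-Whitney if needed. No section gives an enrolment target, an expected loss rate or an allowance for loss. Neither 8.5 nor 8.8 says whether an eliminated subject leaves the analysis.

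**The concern.** A number quoted as delivering 80% power should do so on its own inputs, and 18 is the formula's result rounded down. That alone is a small matter. It carries more weight beside the second gap, because a calculation with no margin is followed by five ways to be eliminated, and the plan does not say whether 18 is counted before or after them.

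What is at stake is how a null result is read. Someone who relies on 80% when weighing a non-significant TCSS difference would overrate what the trial could detect. The error is slight if 18 are evaluable and larger if 18 were enrolled and some were dropped from the analysis.

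**Working it through.** **Inputs, all from 8.4:** SD s = 0.84; difference d = 0.776; Z values 1.96 and 0.84; n = 18 per group. The between-group test comes from 8.8.

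**1. The plan's own figure.** n = 2(Zα + Zβ)²s²/d².

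- 2(1.96 + 0.84)² = 2 × 7.84 = 15.68, as printed.
- 0.84² = 0.7056, as printed.
- 0.776² = 0.6022 (printed as 0.6021).
- 15.68 × 0.7056 / 0.6021 = 18.375, which rounds up to 19. The plan reports 18.

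**2. Power at 18 by the method of 8.4.** d / (s√(2/n)) = 0.776 / (0.84 × √(2/18)) = 0.776 / 0.280 = 2.771. Power = Φ(2.771 − 1.96) = Φ(0.811) = 79.1%. At 19 it is 81.3%.

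**3. Power for the planned t-test.** The noncentrality is the same, 2.771, with 34 degrees of freedom and a critical value of 2.032. Noncentral-t power is 76.8%. Solving for 80% gives 19.40, so 20 per group.

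| Evaluable per group | Normal approximation | t-test |
|---|---|---|
| 18 | 79.1% | 76.8% |
| 19 | 81.3% | 79.1% |
| 20 | 83.2% | 81.2% |

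The 3.2-point t-test gap therefore has two parts: 80 − 79.1 = 0.9 from rounding down, and 79.1 − 76.8 = 2.3 from using a normal approximation for a t-test.

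**4. Effect of eliminations (conditional).** The documents give no loss rate. Assume that 18 is the enrolled number, that eliminated subjects leave the analysis, and that both arms lose equally. Then:

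- 16 left per group (2 of 18 lost, 11%): t-test power 71.5%.
- 14 left per group (4 of 18 lost, 22%): t-test power 65.3%.

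If the loss fell on one arm only, power would be 74.1% (16 against 18) or 70.8% (14 against 18).

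**5. What the baseline score could recover.** Under ANCOVA of final on baseline TCSS the residual SD is 0.84√(1 − r²), where r is the baseline-final correlation. The documents give no value for r. Simulated power at 18 per group, allowing for chance baseline imbalance, is about 79% at r = 0.3, 80.6% at r = 0.35 and 86% at r = 0.5. The closed form that ignores imbalance gives 80.5% at r = 0.3, which is slightly optimistic. So r of about 0.35 is needed to restore 80%. At 16 per group, r = 0.5 gives about 82%.

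**The case against.** The strongest reply is that little has been proven. By 8.4's own method the slip is one patient per group and 0.9 points of power. The figure of 20 is a choice of method: planning a t-test with table Z values is a common approximation and does not contradict 8.8. Both points stand, which is why the t-test figure is offered as a refinement and not as a second arithmetic error. Recruitment was scheduled for 2021 (section 10) and the document is dated March 2025, so changing the sample size is probably moot. That stands too, and it limits the remedy to reporting and analysis.

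Three stronger readings are tempting, and the documents do not support them:

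- **That the trial's real power is 65–72%.** This needs 18 to be the enrolled number, eliminated subjects to be left out of the analysis, and a particular loss rate. The plan settles none of these. What can be shown is an omission.
- **That the formula itself is wrong.** As typeset, only Zβ carries the exponent, which would give about 6 per group. But the printed 15.68 is 2(1.96 + 0.84)², so the sum was squared, and the misplaced exponent may come from reading the PDF.
- **That the SD of 0.84 is too small.** It is borrowed from a trial of another treatment, and the plan does not argue that it carries over to these entry criteria. But the documents offer no other TCSS SD, so no error can be shown.

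**Conclusion.** The point holds in limited form. On the plan's own inputs, 18 per group does not reach the stated 80% power: it gives 79.1% by the method of 8.4 and 76.8% for the planned t-test. The formula gives 19, and the t-test needs 20. This rests only on the figures printed in 8.4 and on 18 being evaluable.

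The silence on enrolled against evaluable numbers, and the absence of any loss allowance, are real omissions. Their cost in power cannot be fixed from the documents; 71.5% and 65.3% illustrate it under the stated assumptions. The two missed-visit rules in 8.5 also disagree: a subject who misses only one intermediate visit is eliminated under one and not under the other. They must be reconciled before any loss rate can be estimated.

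**What to change.** None of the following adds patients.

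1. In 8.4, correct the result to 19 per group by the formula used (20 for the t-test), and restate power at 18 evaluable per group as about 77%.
2. Say whether 18 is enrolled or evaluable, and say in 8.8 whether eliminated subjects leave the analysis. If 18 is enrolled and they leave, give the power at the evaluable number, with loss rates labelled as assumptions. Reconcile the two missed-visit rules first.
3. If allocation is still masked, pre-specify ANCOVA of final TCSS on baseline TCSS as the between-group analysis. The baseline score is already collected. State that restoring 80% at 18 evaluable per group takes a correlation of about 0.35, and that the documents give none.

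Items 1 and 2 cost wording and a less favourable stated power. Given the dates, they may only be possible as corrections in the final report. Item 3 is one analysis choice and should not be made once allocation is known.

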8.5 Selection criteria

Inclusion Criteria	Non-inclusion Criteria

 - Adults aged 40-60 years with a diagnosis of type 2 diabetes mellitus (T2D) and diabetic neuropathy - Minimum duration of T2DM diagnosis: 5 years. - MNSI (Michigan Neuropathy Screening Instrument) score ≥ 2. - Both genders. - Must sign the informed consent form 	
 - Subjects with known sensitivity or hyperreactivity to cocoa or any of its components. - Pregnant women. - Subjects with neurological diseases, such as multiple sclerosis, epilepsy, or previous cerebrovascular events. - Subjects with implanted electronic devices, e.g., pacemakers. - Subjects with peripheral nerve damage in the lower extremities caused by trauma.

	
 - Subjects with a diagnosis of disc herniation below T10. - History/diagnosis of herpes zoster. - Serological diagnosis of rheumatoid arthritis or systemic lupus erythematosus. HIV/AIDS. - Venous insufficiency (C2-C6 class, asymptomatic/symptomatic according to Nicolaides CEAP classification) in lower limbs. - Clinical hypothyroidism. - Use of orthopedic equipment (e.g., prosthetics, splints, wheelchair, crutches). - Cancer diagnosis, use of oncological drugs and/or radiotherapy, or history of cancer or tumors treated with oncological drugs or radiotherapy. - Smoking, considered positive in those with a smoking index greater than 10. - History of diabetic foot (Wagner Scale 3-5) or amputation. - Presence of ulcers and open and/or extensive wounds (>2 cm) - Allodynia - Sciatic nerve root compression - Gout/Hyperuricemia
--	---

Elimination Criteria

- Subjects who modify their pharmacological treatment during the study.
- Subjects who do not attend one of the intermediate consultations
- Subjects who withdraw informed consent or decide not to continue participating in the

study

- Subjects with less than 80% adherence to cocoa supplementation
- Subjects who miss more than one consultation or do not attend the final consultation.

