2.5 Diagnosis

Patients with DM should be evaluated for diabetic neuropathy at diagnosis and for 5 years thereafter, and an annual review is recommended through a detailed clinical history, physical examination, and clinical tests. (14) The diagnosis of DN is made when other causes that could be causing the signs and symptoms are excluded and can be supported by tools such as questionnaires and tests. (16)

Among the causes of neuropathy that must be excluded to make the diagnosis are toxic or drug-induced neuropathy, alcoholic neuropathy, neuropathy associated with HIV, hypothyroidism, and neuropathy due to vitamin B12 deficiency. Especially, those subjects who take metformin as a pharmacological treatment for T2D are at high risk of developing vitamin B12 deficiency since it decreases the absorption of this vitamin in the terminal ileum and is related to alterations in intrinsic factor levels. (28, 29) The signs and symptoms of vitamin B12 deficiency are very similar to those observed in diabetic neuropathy, and therefore, their differentiation can be complex. Thus, the determination of serum vitamin B12 is suggested to exclude non-diabetic causes of neuropathy. (29)

On the other hand, among the tools that can support the diagnosis of DN are biopsy, which is an invasive test; nerve conduction tests, which are expensive and are only useful to evaluate fast conduction fibers, which are not very practical; and the sensory test with the monofilament. (30)

The Michigan Neuropathy Screening Instrument (MNSI) is a validated tool available in Spanish, which evaluates the presence of diabetic peripheral neuropathy. This instrument can be applied quickly, includes the history of symptoms and physical examination to detect alterations in the foot. It has a sensitivity of 65% and specificity of 83%, and a score of ≥ 2 has been proposed as a cut-off point for the diagnosis of DPN. (31, 32)

Another tool that allows the severity of DN to be evaluated is the Toronto Clinical Scoring System (TCSS), which evaluates the symptoms, reflexes, and sensitivity by anatomical

regions. According to the score obtained, 3 grades are established: 0-5 points, no DN; 6-8 points, mild DN, 9-11 points, moderate DN and 12-19 points, severe DN. (33, 34)

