8.6 Study Variables

Type	Variable	Conceptual Definition	Operational Definition	Indicator (unity)	Scale
Independent	Cocoa supplementation	Cocoa powder capsules	4 cocoa powder capsules providing 50 mg of flavonoids (12.5 mg per capsule), administering two capsules in the morning and two capsules at night, every day, for three months. (Appendix 2)	Present (supplement) / Absent (placebo)	Qualitative nominal dichotomous
Dependent	Peripheral diabetic neuropathy	Presence of signs and/or symptoms of peripheral nerve dysfunction in people with diabetes, after excluding other causes. (50)	
It is obtained after applying the MNSI questionnaire regarding symptoms (filled out by the patient and with a maximum score of 13 points) and the physical examination (evaluated by the researcher) with a maximum score of 13 points. (Appendix 3) (51)
 
Toronto Clinical Scoring System: is a clinical evaluation system carried out by the researcher, assigning a score to the symptoms, reflexes and sensory tests. (33, 34) (Appendix 4)
 
H reflex test: This is performed by electrical stimulation, placing the active electrode on the Achilles tendon, the positive electrode above the gastrocnemius and the reference electrode at the height of the gastrocnemius heads. Stimulation is carried out behind the knee (anatomical site of the tibial nerve). The electrical stimulus consists of the application of 10 pulses (1 every 10 seconds) and the maximum intensity applied is according to the sensitivity and tolerance of each individual. (18, 36)
	
Total sum of points obtained from the application of the MNSI questionnaire No unit
 
6-8 points: mild DN 9-11 points: moderate DN 12-19 points: severe DN
 
Total sum of points obtained from the application of the TCSS No unit
 
Quotient R2/R1 μV
	Discrete quantitative Qualitative ordinal Discrete quantitative Discrete quantitative

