Appendix 4: Toronto Clinical Scoring System (TCSS)

Symptom scores	Reflex scores	Sensory test scores
Foot	Knee reflexes	Pinprick
Pain	Ankle reflexes	Temperature
Numbness		Light touch
Tingling		Vibration
Weakness		Position
Ataxia		
Upper-limb symptoms		

Sensory testing was performed on the first toe. Symptom scores: present = 1; absent = 0. Reflex scores: absent = 2; reduced = 1, normal = 0. Sensory test score: abnormal = 1, normal = 0. Total scores range from normal = 0 to maximum of 19.

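### MNSI ≥ 2 is the only neuropathy score that gates entry, so people the protocol's own TCSS grading calls free of neuropathy can be randomised into a trial sized on the TCSS

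*Combined protocol and SAP*

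**What the plan says.** **Entry.** Section 8.5 asks for "Adults aged 40-60 years with a diagnosis of type 2 diabetes mellitus (T2D) and diabetic neuropathy", a diabetes duration of at least 5 years, and "MNSI (Michigan Neuropathy Screening Instrument) score ≥ 2". None of its inclusion, non-inclusion or elimination criteria mentions the TCSS.

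**How neuropathy is established.** Section 8.7 states that "at the beginning of the study the MNSI (Annex 3) will be applied as part of the diagnosis of DN". The same section schedules the TCSS at the start and end of the study, as a measurement and not as a condition of entry. On the MNSI, section 2.5 says: "It has a sensitivity of 65% and specificity of 83%, and a score of ≥ 2 has been proposed as a cut-off point".

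**TCSS grading.** Section 2.5 gives "0-5 points, no DN; 6-8 points, mild DN, 9-11 points, moderate DN and 12-19 points, severe DN". The variable table in 8.6 lists only "6-8 points: mild DN 9-11 points: moderate DN 12-19 points: severe DN", so scores of 0-5 have no category there. Appendix 4 sets the range: "Total scores range from normal = 0 to maximum of 19".

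**Sizing.** Section 8.4 uses the TCSS, with SD 0.84 taken from a cited study in people with neuropathy and a difference of 0.776, which "refers to the expected difference → 7.5% decrease with respect to the control group". It arrives at 18 per group.

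**The concern.** The scale that defines the target effect plays no part in selecting the people in whom that effect is sought. A participant can satisfy 8.5 and still be graded as having no neuropathy on the trial's own TCSS cut-offs.

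Two things are at stake. The first is interpretation: if the TCSS shows no difference between arms, it will be unclear whether cocoa failed or whether part of the sample had little neuropathy on that scale to begin with. The second is power: low scorers would shrink the mean difference if the effect is proportional, and would widen the spread of scores beyond what section 8.4 assumes.

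**Working it through.** **1. Reproduce the plan's figure.** Inputs from section 8.4: s = 0.84, d = 0.776, Zα = 1.96, Zβ = 0.84.

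n = 2(1.96 + 0.84)² × 0.84² / 0.776² = 15.68 × 0.7056 / 0.6022 = 18.37, stated as 18 per group. With a t-test at 18 per group, power is 76.8%.

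**2. The population this assumes.** If 0.776 points is 7.5% of the control mean, that mean is 0.776 / 0.075 = 10.35, which section 2.5 grades as moderate. With SD 0.84, the boundary between 5 and 6 (taken as 5.5) lies (10.35 − 5.5) / 0.84 = 5.8 SD below the mean. The sizing therefore allows for essentially nobody at 0-5.

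**3. The population that can enter.** No rule stops a score of 0-5. Appendix 3 shows one route. Item 9 asks whether a doctor has told the person that they have diabetic neuropathy, and item 14 asks about dry, cracking skin on the feet. Neither is a component of the TCSS in Appendix 4. If each counts one point and the cut-off applies to the questionnaire, these two answers reach MNSI 2 and add nothing to the TCSS. Section 8.5 does not say whether the cut-off refers to the questionnaire or to the physical examination.

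**4. Contribution under a proportional effect.** 7.5% of a score of 0, 1, 3 or 5 is 0, 0.075, 0.225 or 0.375 points. The largest, 0.375, is under half of 0.776.

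**5. Illustrative power.** Let a share f enter with mean TCSS 3 and the rest average 10.35. Both f and the value 3 are assumptions; the documents give neither. Mean difference = (1 − f) × 0.776 + f × 0.225. Power is for a two-sided t-test at 5%, 18 per group, SD held at 0.84.

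| f | Mean difference | Power |
|---|---|---|
| 0% | 0.776 | 77% |
| 20% | 0.8 × 0.776 + 0.2 × 0.225 = 0.666 | 64% |
| 40% | 0.6 × 0.776 + 0.4 × 0.225 = 0.556 | 49% |

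**6. The spread, with and without a TCSS minimum.** Holding SD at 0.84 is generous. In the 20% case, a simple two-group mixture has SD = √(0.84² + 0.2 × 0.8 × (10.35 − 3)²) = 3.06, and power is about 10%. But a wide spread does not depend on low scorers. If scores were spread evenly over whole numbers from 6 upwards (again an assumption), with SD = √((k² − 1)/12) for k values and a difference of 0.776:

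| Range | k | SD | Power at 18 per group |
|---|---|---|---|
| 6-12 | 7 | 2.0 | 20% |
| 6-15 | 10 | 2.9 | 12% |
| 6-19 | 14 | 4.0 | 9% |

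**The case against.** **Entry is not by MNSI alone.** A reader might infer that anyone scoring 2 gets in. Section 8.5 also requires a diagnosis of diabetic neuropathy and 5 years of diabetes, and section 2.5 describes that diagnosis as made after other causes are excluded. This stands and narrows the point. It does not remove it, because the MNSI is itself part of how the diagnosis is made and no TCSS condition is attached to it.

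**Low scorers are not all at the floor.** A reader might infer that they have almost no room to improve. That is true only at 0. A score of 1 can fall by 1.3 times the 0.776 target (1 / 0.776) and a score of 5 by 6.4 times (5 / 0.776). The dilution comes from assuming a proportional effect. If the effect were a constant 0.776 points, people scoring 1-5 would not reduce the mean difference. This stands.

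**The share of low scorers is unknown.** It is tempting to estimate it from the MNSI's 65% sensitivity and 83% specificity with the 29-95% neuropathy prevalence in section 2.3. That prevalence describes people with diabetes in general, not people already diagnosed with neuropathy, and the documents never relate the MNSI to the TCSS. No share can be derived.

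**The 10% power figure should not be blamed on the missing TCSS minimum.** It rests on an assumed two-cluster distribution, and step 6 gives similarly low power with every score at 6 or above. This stands.

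**The TCSS is not declared primary.** Section 7.1 lists it beside biochemical, quality-of-life, gastrointestinal and H-reflex objectives, so a TCSS minimum would narrow the population for all of them. This is a fair cost. The TCSS is nevertheless the only outcome used for sizing.

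**Conclusion.** The point holds as a mismatch between entry and sizing. People with a baseline TCSS of 0-5 can be randomised, the protocol grades them as without neuropathy, the 8.6 scale has no place for them, and section 8.4 assumes a narrow group with mean about 10.35 and SD 0.84.

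The size of the harm cannot be fixed from the documents. Under a proportional 7.5% effect, each such person contributes 0-0.375 points against 0.776. The fall in power from 77% to 64% rests on that effect model, on an assumed 20% share at mean TCSS 3, and on SD staying at 0.84. It shows the direction and is not an estimate.

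The change is worth making because it is cheap and uses the protocol's own threshold. It would not rescue the sample size: the sizing SD and the unadjusted month-3 comparison in section 8.8 need their own correction.

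**What to change.** Add to the inclusion criteria in 8.5 a baseline TCSS of at least 6, the protocol's own lower limit for neuropathy. Score the TCSS before randomisation, at the baseline visit where it is already scheduled. Keep MNSI ≥ 2 as the first screen, and state whether that cut-off refers to the questionnaire or the physical examination.

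Costs:
- One line of text, some screen failures and slower recruitment.
- A narrower population for the biochemical, quality-of-life, gastrointestinal and H-reflex outcomes.
- Regression to the mean. Selecting on a high baseline score can make both arms appear to improve in the within-arm paired tests planned in 8.8. It does not bias the randomised comparison, so the conclusion should rest on the between-arm result.

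If enrolment has already closed, report by arm how many entered at TCSS 0-5 and add a baseline-adjusted between-arm analysis of the TCSS.
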